## PROTOCOL TITLE: Manual vs. custom knee study

### 1. Objectives

1. To determine whether the low-dose, biplanar x-ray imaging (EOS) has the same accuracy as computed axial tomography (CT)
2. To validate low-dose, biplanar x-ray imaging (EOS) as a tool to evaluate 3-dimensional alignment of Total Knee Replacement implants.
3. To evaluate differences in total knee replacement implant alignment in patients whose arthroplasty is performed using manual or custom instrumentation derived from preoperative CT

### 2. Background

Achieving optimal prosthetic alignment of the femoral, tibial and patellar components during Total Knee Replacement (TKR) is of great importance as it contributes to better function, less pain and improved quality of life. TKR requires accuracy in the execution of bone cuts in the correct orientation to the coronal, sagittal and axial planes. Malposition potentially leads to increased mechanical stress on the bearing surfaces and inevitably to earlier loosening.

Computed Axial Tomography (CT) is the gold standard technique to evaluate implant alignment in the coronal, sagittal and axial planes. As such, CT has imaging been used to create custom instrumentation with purported likely improvement in surgical outcomes. Customized instrumentation created from a preoperative CT has been shown to be safe and effective, with no reported difference in patient outcomes and similar total knee arthroplasty component alignment. However, taking into consideration CT's high levels of radiation, cost expenses and its inability to obtain images of the limb in weight-bearing position, CT scan cannot be used routinely as a postoperative tool to evaluate TKR implant positioning.

The imaging system manufactured by EOS Imaging (formerly Biospace Med, Paris) is a biplanar, low-dose radiation, full body, high resolution, radiological imaging system allowing simultaneous acquisition in the coronal and sagittal planes and in standing position. EOS' main benefits are the considerable reduction in radiation dose (up to 1000 times less than for CT and ten times less than the plain radiography) by using a gaseous detector. George Charpak, the inventor, was awarded the Nobel Prize in 1992 for this work. Moreover, the EOS system can provide 3D images by using the appropriate software algorithms, thus providing a low-radiation alternative to CT.

### 3. Inclusion and Exclusion Criteria

#### 3.1 INCLUSION CRITERIA:

- Radiographically confirmed diagnosis of osteoarthritis (OA)
- Failure of non-operative treatment for the diagnosis of symptomatic Osteoarthritis
- Age greater than 18 years
- Desire to proceed with elective TKR
- Completion of informed consent and signature of written consent form

#### 3.2 EXCLUSION CRITERIA:

- Ligamentous instability that may necessitate a constrained TKR implant

**PROTOCOL TITLE:** Manual vs. custom knee study

- Retained hardware in the distal femur or proximal tibia of the operative extremity
- Medical contraindication to undergo preoperative CT, or inability to tolerate preoperative CT

**4. Study-Wide Number of Subjects**

112

**5. Study-Wide Recruitment Methods**

Subjects will be enrolled in the study in the Northwestern Medicine outpatient orthopaedic surgery clinic [[name]] at their pre-operative clinical appointment with either [name] or [name]. The principal investigator or sub-investigator will complete the informed consent process and obtain the written consent form.

**6. Multi-Site Research**

N/A

**7. Study Timelines**

1.1. All subjects will follow the time points below:

- Baseline (pre-operative)
- 6 weeks post-operative
- All primary analyses of the study will be completed by 2015.

**8. Study Endpoints**

1. To determine whether the low-dose, biplanar x-ray imaging System (EOS) has the same accuracy as CT in the evaluation of TKR implants
2. To validate EOS as a tool to evaluate 3-Dimensional alignment of TKR implants in the coronal, sagittal and axial planes
3. Evaluate differences in component alignment of patients whose arthroplasty is performed by using manual or custom instrumentation derived from a preoperative CT scan.

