**9. Procedures Involved**

Subjects will undergo standard of care preoperative low-dose, biplanar x-ray (EOS) and standard of care preoperative CT of the surgical extremity. All subjects' preoperative standard of care CT will be used for surgical planning of bony resection during total knee replacement. They will then be randomized in a single-blinded fashion into one of four groups: Group A, using customized instrumentation derived from preoperative CT for both the femoral and tibial preparation; Group B, using customized instrumentation derived from the preoperative CT for the femoral preparation and manual instrumentation for the tibial preparation; Group C, using manual instrumentation for both the femoral and tibial preparation; and Group D, using customized instrumentation derived from the preoperative CT for the tibial preparation and manual instrumentation for the femoral preparation. The 4th randomization arm is being added in order to

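### The endpoints on EOS accuracy and validation for knee implants have no reference measurement, because CT is taken only before surgery; the preoperative EOS-CT pairs exist but have no planned agreement analysis

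*Combined protocol and SAP*

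**What the plan says.** All references are to the combined protocol and SAP.

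- **Aims for implants.** Section 8 gives endpoint 1 as "To determine whether the low-dose, biplanar x-ray imaging System (EOS) has the same accuracy as CT in the evaluation of TKR implants" and endpoint 2 as "To validate EOS as a tool to evaluate 3-Dimensional alignment of TKR implants in the coronal, sagittal and axial planes". Objective 2 in Section 1 matches endpoint 2: "To validate low-dose, biplanar x-ray imaging (EOS) as a tool to evaluate 3-dimensional alignment of Total Knee Replacement implants".
- **Objective 1.** Section 1 asks whether EOS is as accurate as CT and does not mention implants.
- **Reference standard.** Section 2 calls CT the gold standard for implant alignment. It then says "CT scan cannot be used routinely as a postoperative tool to evaluate TKR implant positioning", and among the reasons gives "its inability to obtain images of the limb in weight-bearing position".
- **Imaging before surgery.** Section 9: "Subjects will undergo standard of care preoperative low-dose, biplanar x-ray (EOS) and standard of care preoperative CT of the surgical extremity". The CT is used to plan the bone cuts and to derive the custom instruments.
- **Imaging after surgery.** Section 7 lists one postoperative time point, "6 weeks post-operative". Section 9 also lists a three-week visit but describes no imaging there. The six-week image is EOS.
- **Comparison and readings.** Sections 9 and 11 compare postoperative alignment with the preoperative CT plan. The EOS manufacturer measures both the preoperative and the postoperative radiographs, which are sent de-identified.
- **Analysis.** Section 11 gives a Wilcoxon rank-sum test between groups for alignment, and a t-test between groups for operative time and blood loss. It gives nothing else.

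**The concern.** A claim that one imaging method is as accurate as another, or is validated against it, needs both methods applied to the same object. For implants the plan has only one of them. The one comparison it does make after surgery is EOS against the surgical plan. If that were reported as validation, accurate surgery would make EOS look accurate and inaccurate surgery would make EOS look poor.

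For objective 1 the position differs. The paired images exist, but nothing in the analysis section uses them, so that objective would end without a planned answer.

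**Working it through.** **The plan's own figure.** There is none on this point. The only sample-size statement (25 per group, 28 planned, in Section 11) is for a 1 degree difference between instrumentation groups. No margin, agreement method or sample size is given for EOS against CT.

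**Each aim traced to its data.**

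| Aim | Images of the same object | Reference | Planned analysis |
|---|---|---|---|
| Endpoints 1 and 2, objective 2 (implants) | EOS at six weeks only | None; the CT plan predates the implant | None |
| Objective 1 (EOS against CT, implants not named) | Preoperative EOS and CT, native knee | CT | None |
| Objective and endpoint 3 (manual or custom) | EOS at six weeks, set against the plan | Not needed for a between-group contrast | Wilcoxon between groups |

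**Why EOS minus plan cannot validate EOS.** For any one angle, let P be the planned value, T the true implant position and M the postoperative EOS reading. Then

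M − P = (T − P) + (M − T) = surgical deviation + EOS error.

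Only M and P are observed. The mean of M − P is the sum of two unknown means, and its variance is the sum of two unknown variances plus twice an unknown covariance. A mean of 0 fits no surgical deviation with no EOS bias equally well as +1 degree of surgical deviation with −1 degree of EOS bias. More subjects estimate the sum more precisely but do not split it. Objective 3 asks whether alignment differs by instrumentation, so the protocol cannot also take surgical deviation to be zero.

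**Readings for objective 1.** Sections 9 and 11 assign the preoperative radiographs to the EOS manufacturer. They describe no matching reading on the CT and no angle definition common to both. De-identification protects identity; it is not a rule that a reading be made without sight of the plan or of the other method.

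**What the preoperative pairs could give (illustration only).** The documents give no SD for EOS-CT differences, so SDs of 1.0, 1.5 and 2.0 degrees are assumed. The 1.5 degrees in Section 11 is a different quantity (axial alignment with custom instrumentation).

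- Half-width of the 95% CI for mean bias: t(0.975, n−1) × SD / √n.
- Half-width for each limit of agreement: t(0.975, n−1) × SD × √(1/n + 1.96² / (2(n−1))).

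| Pairs | Quantity | SD 1.0 | SD 1.5 | SD 2.0 |
|---|---|---|---|---|
| 112 | Bias | 0.19 | 0.28 | 0.37 |
| 112 | Limit of agreement | 0.32 | 0.48 | 0.64 |
| 80 | Bias | 0.22 | 0.33 | 0.45 |
| 80 | Limit of agreement | 0.38 | 0.57 | 0.76 |

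The row for 80 is a lower case, taken from the 20 enrolled plus 60 remaining that Section 9 mentions. These figures describe the proposed analysis. They do not measure the defect, which is structural.

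**The case against.** **The trial is built for the instrumentation comparison.** Section 11 makes component alignment the primary outcome and sizes the study for the between-group contrast. No sentence says that EOS-versus-plan differences will be called validation. This stands as a limit on the point: objective 3 can still be addressed. It does not rescue the aims listed first in Sections 1 and 8, which the design cannot meet for implants.

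**The CT plan is the reference.** This fails, because the plan was made before the component was placed. Section 14 mentions CT scans among the risks in general terms but schedules none after surgery.

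**Preoperative EOS readings are provided for.** This stands. With no implant present, the wording about implant measures on preoperative films is most naturally loose wording for native alignment. What is missing is the CT reading and the shared angle definitions.

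**Native-bone agreement is not clearly what the sponsor meant.** Endpoint 1 may simply be the fuller wording of objective 1. That is fair, and it is why the agreement analysis below is conditional. Removing the implant claims would by itself cure the contradiction.

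**Stronger readings that the documents do not support.**

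- A reader might infer that unvalidated EOS readings invalidate objective 3, or the reverse, that a constant EOS offset is harmless there. Neither follows. An offset cancels between groups if signed deviations are compared. It need not cancel for absolute deviations: with an offset of +1 degree, true deviations of +1 and −1, equal in size, become 2 and 0. The documents do not say which is analysed.
- A reader might also infer a definite loss of power from random EOS error. That depends on whether the 1.5 degree SD already contains measurement error, which the documents do not say, so no figure is claimed.

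**Conclusion.** The point holds and needs correction before the study's claims are final. Endpoints 1 and 2 and objective 2 set out to show accuracy equal to CT, or validation, for implants, with zero EOS-CT pairs of an implant and no other independent measurement of implant position. This rests only on the imaging schedule and the comparator as written, not on any assumed number, and no later analysis of the planned data can repair it. Objective 1 has up to 112 native-knee pairs but no planned analysis, no described CT reading and no common angles. The part that must change is the implant claims. The agreement analysis is the way to keep an imaging aim if one is wanted.

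**What to change.** 1. **Sections 1 and 8.** Remove the claims of equal accuracy and of validation for TKR implants. State that EOS-versus-plan differences will be reported as deviation from plan and not as validation of EOS.
2. **If an imaging aim is kept.** Restate it as agreement between preoperative EOS and preoperative CT on the same native-bone angles. Define each angle within one bone, because EOS is taken standing and CT is not weight-bearing. State that this agreement need not carry over to implants.
3. **Section 11, with item 2.** Add a Bland-Altman analysis for each angle, giving mean bias and 95% limits of agreement with confidence intervals. Have EOS and CT each read without sight of the other or of the plan, including the manufacturer's readings. Any statement of equivalence would need a margin set and justified in advance.

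**Cost.** Rewording of Sections 1, 8 and 11; for items 2 and 3, a written reading procedure, reading time on scans already taken and one paired analysis. No new scan is needed. The downsides are a narrower claim that says nothing about implant measurement, and precision that depends on how many complete pairs are obtained.

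Keeping an implant-validation claim would instead need an independent postoperative reference measurement. Section 2 argues against routine postoperative CT and Section 14 notes that radiation exposure adds up, so that decision is left to the investigators and the IRB.

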**9. Procedures Involved**

Subjects will undergo standard of care preoperative low-dose, biplanar x-ray (EOS) and standard of care preoperative CT of the surgical extremity. All subjects' preoperative standard of care CT will be used for surgical planning of bony resection during total knee replacement. They will then be randomized in a single-blinded fashion into one of four groups: Group A, using customized instrumentation derived from preoperative CT for both the femoral and tibial preparation; Group B, using customized instrumentation derived from the preoperative CT for the femoral preparation and manual instrumentation for the tibial preparation; Group C, using manual instrumentation for both the femoral and tibial preparation; and Group D, using customized instrumentation derived from the preoperative CT for the tibial preparation and manual instrumentation for the femoral preparation. The 4th randomization arm is being added in order to

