**11. Data and Specimen Management**

The primary outcome measure of total knee arthroplasty component alignment will be measured on the postoperative EOS image obtained at the six week follow-up appointment. Alignment will be measured in the coronal, sagittal and axial planes and compared to the preoperative plan created with the preoperative CT. All TKR implant alignment measures for both the pre and post op radiographs will be done by the manufacturer of the EOS Imaging system. All radiographs sent to EOS Imaging will be fully de-identified and will be

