**PROTOCOL TITLE: Manual vs. custom knee study**

transmitted securely using Box.com in a dicom format.

Secondary outcomes of operative time and intraoperative blood loss will be obtained from the medical record. Wilcoxon Rank-Sum test will be used to compare the coronal, sagittal, and axial alignment measurements between groups. Student's t-test will be used to compare the secondary outcome measures of operative time and intraoperative blood loss between groups.

A power analysis was performed to determine appropriate sample size for each group to determine a 1 degree difference in component alignment. Previous literature has noted standard deviation in axial alignment with custom instrumentation is 1.5 degrees. With a p-value of 0.05 and a power of 0.8, our power analysis determined that each group needed to include 25 subjects to be appropriately powered. The planned sample size of 28 subjects in each group was chosen to fulfill this power analysis.

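### The primary alignment comparison has no baseline covariate although a preoperative EOS image exists for every subject; this may give up precision, by an amount the documents do not let one fix

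*Combined protocol and SAP*

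**What the plan says.** Section 9 (Procedures Involved) has every subject undergo a "standard of care preoperative low-dose, biplanar x-ray (EOS" examination and a preoperative CT, and places randomisation after both. Section 11 (Data and Specimen Management) says that "All TKR implant alignment measures for both the pre and post op radiographs" are made by the manufacturer of the EOS system; Section 9 says the same.

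The primary outcome is component alignment on the 6-week EOS image in three planes, set against each patient's own CT-based plan. The analysis in Section 11 is one sentence: "Wilcoxon Rank-Sum test will be used to compare the coronal, sagittal, and axial alignment measurements between groups". No covariate is named for any comparison, and no use is stated for the preoperative EOS readings.

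The sample size in Section 11 is set "to determine a 1 degree difference in component alignment", on the basis that the "standard deviation in axial alignment with custom instrumentation is 1.5 degrees". It is worked "With a p-value of 0.05 and a power of 0.8", and the text concludes that "our power analysis determined that each group needed to include 25 subjects to be appropriately powered". It adds: "The planned sample size of 28 subjects in each group was chosen to fulfill this power analysis".

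**The concern.** A measurement taken before randomisation that predicts the outcome can be used to remove part of the outcome's spread, and to correct for chance differences between small groups. Here the image is already planned for everyone. If a knee with more preoperative deformity is harder to bring to its planned alignment, part of the 6-week variation is predictable, and an unadjusted test leaves it in the error term.

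What is at stake is precision, not validity: the unadjusted rank-sum test remains valid under randomisation. Precision matters here because, on the stated inputs, 28 per group falls short of 80% power for a two-sided comparison of two groups. An adjustment chosen only after the results have been seen would also carry little weight, so the time to decide is before the groups are compared.

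**Working it through.** **Inputs from Section 11.** Difference 1 degree; SD 1.5 degrees (axial plane, custom instrumentation); alpha 0.05; power 0.80; 25 per group required, 28 planned. Sidedness is not stated; two-sided is assumed.

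**Input not in the documents.** The correlation r between preoperative native alignment and the analysed outcome. A range of 0 to 0.5 is assumed.

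**Step 1: the plan's own figure.** For two means, n per group = 2 × [1.5 × (1.960 + 0.842) / 1]² = 35.3, so 36. The stated 25 is not reproduced. The exact t-test gives 36.3. A one-sided 0.05 gives 28, the planned size, but the plan does not say one-sided. A four-group one-way ANOVA with two means at 0 and two at 1 degree gives 25.5, but the plan names no ANOVA. This is a separate matter; it is shown here only to fix the starting power.

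**Step 2: power without a covariate.** With 28 per group the noncentrality is (1/1.5) × √(28/2) = 2.494 on 54 degrees of freedom, which gives two-sided t-test power of 68.8%. (A normal approximation gives 70.3%.)

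**Step 3: power with a covariate.** Residual SD = 1.5 × √(1 − r²). The equivalent sample multiplier is 1/(1 − r²).

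| Assumed r | Residual SD (degrees) | Power, 28 per group | Gain (points) | Sample multiplier |
|---|---|---|---|---|
| 0 | 1.50 | 68.8% | 0 | 1.00 |
| 0.1 | 1.49 | 69.2% | 0.4 | 1.01 |
| 0.2 | 1.47 | 70.6% | 1.8 | 1.04 |
| 0.3 | 1.43 | 72.8% | about 4 | 1.10 |
| 0.4 | 1.37 | 76.2% | about 7 | 1.19 |
| 0.5 | 1.30 | 80.8% | about 12 | 1.33 |

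Reaching 80% at 28 per group needs r of about 0.49. If the effective sample size is scaled by the rank-sum test's efficiency of 0.955 under normality, r = 0.5 gives about 79%.

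**Step 4: the cost if r is zero.** Losing one degree of freedom (54 to 53) costs under 0.1 point. Allowing also for chance imbalance in the covariate, the variance of the adjusted difference rises by a factor of about 1 + 1/(56 − 4) = 1.019, and power falls from 68.8% to 67.9%, about 1 point.

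**The case against.** The strongest case against has four parts.

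- **The covariate is not a baseline of the outcome.** There is no implant before surgery, so the preoperative image can show only native limb alignment, and the documents do not say what is read from it. A preoperative axial reading is not promised, although the power figure concerns the axial plane. This stands. A covariate need only predict the outcome, but r may well be modest, and the reading must be defined.
- **The outcome is set against each patient's own plan.** If deviation from plan is analysed, some anatomy is already accounted for and r may be near zero. This stands in part. Subtracting the plan removes the target, not differences in how hard it is to reach. The analysis sentence also does not say whether raw alignment or deviation is tested.
- **Signed alignment does not fit the argument.** If varus and valgus knees are both harder, the relation to signed alignment is U-shaped, and a linear or monotone adjustment recovers little. This stands, and it decides the form of the covariate.
- **The reading may not precede surgery.** Section 14 places the EOS alignment analyses after surgery and postoperative care. The image precedes randomisation, but the documents do not show that the reading does. The radiographs are sent de-identified, but blinding of the reader to allocation is not stated.

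A reader might infer that the plan certainly loses power, or that adjustment would bring 28 per group up to 80%. The documents support neither: they give no r, and 80% is reached only near the top of the assumed range.

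**Conclusion.** The point holds conditionally. The images exist for all subjects, measurement of the preoperative radiographs is planned, and the primary test uses none of it. Prespecified adjustment has a small downside (at most about 1 point of power at r = 0) and an upside that ranges from negligible (under 2 points at r of 0.2 or less) to about 12 points at r = 0.5.

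These figures rest on an assumed r, a two-sided two-group t-test, 28 per group, and an SD of 1.5 degrees that the plan gives for the axial plane only; they need not carry over to the coronal or sagittal comparisons. The shortfall against 80% is a sample-size question that adjustment should not be relied on to solve.

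**What to change.** In Section 11, before any comparison of alignment by group:

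1. State whether the analysed outcome is signed alignment, signed deviation from plan, or absolute deviation from plan.
2. Define the preoperative EOS reading as native limb alignment on the image taken before randomisation, and require that it be read without knowledge of allocation.
3. Prespecify that each alignment comparison is adjusted for that reading, by Quade rank ANCOVA (which keeps the rank basis already chosen) or a linear model.
4. Match the covariate to the outcome: signed preoperative alignment for a signed outcome, size of the preoperative deformity for an absolute deviation. Use the same-plane reading where one exists, and coronal deformity otherwise.
5. Keep the unadjusted rank-sum test as a supportive analysis.

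The cost is a change of wording, about one degree of freedom per comparison and slightly more analysis work. No new images or patients are needed. The manufacturer's reading instructions may need to name the preoperative measurement and the blinding, since the protocol leaves both open.
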